1.2 Secondary Objectives

We will compare the effect of two different LBP pathways on sleep quality, as measured by PROMIS Short Form scores. We will also determine participant characteristics associated with greater improvements in pain and function, and better adherence to each care pathway. Planned and appropriately powered subgroup analyses for treatment moderators of previous opioid exposure and chronic vs. acute LBP will be completed. We will identify multidimensional subgroups from baseline characteristics for treatment moderation of pain and function, as well as for care strategy adherence. These additional analyses will inform the potential for identifying subgroup characteristics that indicated better clinical outcomes for Veterans in either care pathway.

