9.2 Sample Size and Randomization

In **Table 8** below we present a range of minimum detectable effect size differences for the primary outcomes of Pain Interference or Function Scores for both the administrative sample (N=84 per clinic) and survey sample (N=42 per clinic) for 16 clinics (8 clinics randomized to each arm) for Aim 1. Sample size calculations for the cluster randomized design were based on the net difference between the two conditions across baseline and 3-months follow-up.⁵⁰ We assumed over time correlations of 0.50 for both patients (based on data from the [name] et al. pilot study³³ and summary data available for Durham VA clinics, intraclass correlation coefficients (ICC) of 0.01, 0.02, and 0.05 to account for clinic clustering, and also adjusted for the potential group-level randomization of up to 4 stratification variables as baseline covariate adjustments where we conservatively assumed no reduction in either group or subject level variance components. For all calculations, the type-I error is 2.5% to account for the multiple primary outcomes and power is conservatively assumed to be 90% to guard against deviations from assumptions. The number needed at baseline (N_b) is based on an attrition rate of 20%. Note in the **below Table 4** that the scenarios above lead to having adequate power to detect a medium effect size for the primary outcomes for both the administrative and survey samples.

Table 8. Minimum detectable effect size differences for 90% power, alpha of 0.025 and ICC of 0.01, 0.02, and 0.05 for administrative outcome (n=84 per clinic) and survey outcome (n=42 per clinic)

Number of clinics per condition	Number of patients per clinic needed at post-intervention follow-up (Total N)	Minimum Detectable Effect Size Difference ICC=0.01	Minimum Detectable Effect Size Difference ICC=0.02	Minimum Detectable Effect Size Difference ICC=0.05	Number of patients per clinic needed at baseline with 20% attrition (Total N_b)
8	42 (N=672)	0.37	0.42	0.55	53 (N_b =848)
8	84 (N=1344)	0.30	0.36	0.50	105 (N_b =1680)

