9.3 Definition of Populations

As this is an embedded pragmatic trial, all adult subjects that present to clinics with LBP and are referred to one of the two arms of the trial with initial contact with pain navigator or central delivery for data collection will be eligible for the primary analysis as part of the administrative sample. A subset of these Veterans will be enrolled as research subjects so that more detailed research data can be collected at regular intervals for follow up. For this subgroup, equivalent numbers of Veterans with LBP will be enrolled at each clinic.

The primary analyses will be conducted on an intention-to-treat basis; patients will be analyzed in the group to which they were randomized, regardless of intervention adherence, using all available data. The main conclusions drawn from this trial will be based on the pre-specified hypotheses outlined below and will be tested with two-sided p-values at the standard 0.05 level, except where noted due to multiple primary outcomes. For all study outcomes, we will interpret differences between groups over time with reference to prior literature regarding clinically meaningful changes. Results from exploratory analyses will be interpreted with appropriate consideration for their exploratory nature. Statistical analyses will be performed using the latest release of SAS for Windows (Cary, NC) and R software.

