$\beta_1^*(\text{moderator}) + \beta_2^*(\text{moderator}^*\text{intervention}) + \beta_3^*(\text{followup}) + \beta_4^*(\text{followup}^*\text{intervention}) + \beta_5^*(\text{moderator}^*\text{followup}) + \beta_6^*(\text{moderator}^*\text{intervention}^*\text{followup})$ for clinic i , patient j , at time k . A random effects (clinics and time by clinics) will be included in the model to account for clustering of patients within clinics, as the clinics are the unit of randomization. Differential change in pain interference or function by moderator for the two intervention groups is supported if the coefficient for β_6 is significantly different than zero at the $p=0.025$ level. For the adherence multinomial outcome, we will fit a generalized linear model with a random effect for clinic and cumulative logit link function. As the adherence outcome is potentially a 3-level outcome there will be two interaction terms to examine for moderation effects (e.g. whether the effect of the intervention by chronicity is different for those moderately adherent vs. not adherent and/or those fully adherent vs. not adherent).

Exploratory analyses to identify multidimensional subgroups from combinations of baseline characteristics (e.g. age, sex, opioid use) for treatment moderation of the primary outcomes of pain and function as well as per protocol adherence to treatment.

Patients are likely to vary in treatment response. This variation is known as heterogeneity of treatment effects (HTE). Exploration of HTE has typically focused on one-factor-at-a-time post-hoc subgroup analyses (as described in our planned subgroup analysis); however, it is possible to instead identify multidimensional subgroups exhibiting HTE. In particular, we will apply the data-driven method GUIDE⁶⁶(Generalized, Unbiased, Interaction Detection and Estimation) that can be used for longitudinal outcomes, so can incorporate all follow-up outcomes at 3 and 12-months, as well as multi-response outcomes. GUIDE uses a regression tree algorithm that identifies subgroups with heterogeneous effects and estimates how the treatment effect varies across the subgroups. We will include baseline demographic (e.g. age, sex, race) and clinical characteristics (e.g. LBP chronicity, opioid use, comorbid conditions) that are available from EHR. GUIDE provides bootstrap confidence intervals for the treatment effects of identified nodes and is available via a software package.

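### The Aim 2 moderator test (beta_6) has no clinic-level random effect for the moderator, so its 0.025 level holds only if moderator effects do not vary between clinics within an arm, and Table 9 describes a different test

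*Combined protocol and SAP*

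**What the plan says.** Section 9.6 (Aim 2 Analyses) takes the Aim 1 mixed model and adds the moderator and its interactions with intervention and follow-up. The clustering provision is: "A random effects (clinics and time by clinics) will be included in the model to account for clustering of patients within clinics". The decision rule declares moderation when the three-way coefficient, beta_6, meets this criterion: "is significantly different than zero at the $p=0.025$ level". Section 9.3 makes tests two-sided. No random effect involving the moderator is named anywhere. The Aim 1 text lets AIC choose among random-coefficient structures, but its examples are a random intercept and a random linear slope.

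The moderators are patient-level: chronic versus acute pain, and prior opioid exposure. Section 1.2 presents the analyses in strong terms: "Planned and appropriately powered subgroup analyses for treatment moderators of previous opioid exposure and chronic vs. acute LBP will be completed". Section 9.2 supplies Table 9 for them, with 8 clinics per arm, an effective 21 patients per clinic, alpha 0.025 and 90% power. It uses "intraclass correlation coefficients (ICC) of 0.01, 0.02, and 0.05 to account for clinic clustering". The detectable interactions are 0.48, 0.53 and 0.63 SD.

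**The concern.** Beta_6 is a cross-level interaction. One factor (pathway) is fixed for a whole clinic and the other (the moderator) varies inside it. Within each clinic the data give one estimate of how much more one subgroup changes than the other, and beta_6 contrasts the average of 8 such estimates with the average of 8 others. The error term should therefore include how much those clinic-specific effects differ between clinics of the same arm.

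The clinic and time-by-clinic effects do not supply that error. Each shifts a clinic's two subgroups by the same amount and largely drops out of the difference between them. What remains is patient-level error with more than 1,000 degrees of freedom.

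Variation between clinics is plausible from the protocol itself. Section 2.3 lets the type of pain treatment differ by site, section 2.4 leaves the services received in the coordinated pathway uncontrolled, and the Précis expects more variable care in that arm. Section 3 intends the subgroup results to guide how resources are targeted. An understated standard error would give moderation findings too readily and intervals that are too narrow.

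**Working it through.** **Inputs from the documents.** g = 8 clinics per arm; 84 completers per clinic; even moderator split, so m = 84 x 0.5 x 0.5 = 21; over-time correlation 0.5; ICC 0.01/0.02/0.05; alpha 0.025 two-sided (section 9.6, with 9.3); power 90%; 5 degrees of freedom for clinic covariates (Table 7), so 14 - 5 = 9.

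**Input not in the documents.** tau^2, the between-clinic variance of the moderator's effect on change (in SD^2). I write tau^2 = 2 x ICC x (1 - r), where r is the correlation between a clinic's change effects in its two subgroups, and show a range of r.

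**Step 1: scale.** With over-time correlation 0.5, a patient's change has within-clinic variance 2(1 - ICC)(0.5) = 1 - ICC. Clinic mean change has variance 2 x ICC x 0.5 = ICC.

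**Step 2: reproduce Table 9.** Detectable effect = (t[0.9875, 9] + t[0.90, 9]) x sqrt(4[(1 - ICC)(0.5) + m x ICC x 0.5]/(m g)), with t-sum 2.685 + 1.383 = 4.068.

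- ICC 0.01: 4.068 x sqrt(4 x 0.600/168) = 4.068 x 0.1195 = 0.486 (stated 0.48)
- ICC 0.02: 4.068 x sqrt(4 x 0.700/168) = 4.068 x 0.1291 = 0.525 (stated 0.53)
- ICC 0.05: 4.068 x sqrt(4 x 1.000/168) = 4.068 x 0.1543 = 0.628 (stated 0.63)

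The first cell fits 10 df slightly better (0.479), which is a rounding-level difference.

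**Step 3: what Table 9 contains.** The variance under the root equals (2/8)[ICC + (1 - ICC)/21]. With clinic heterogeneity, the variance of beta_6 is (2/8)[tau^2 + (1 - ICC)/21]. So Table 9 corresponds to tau^2 = ICC (r = 0.5) on clinic-level df.

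**Step 4: what the section 9.6 model contains.** Without tau^2 the variance is (2/8)(1 - ICC)/21, giving SEs of 0.1086/0.1080/0.1063. With normal quantiles (2.241 + 1.282 = 3.523) the detectable effects are 0.38/0.38/0.375, almost flat in ICC.

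**Step 5: actual level of the test as written.** Level = 2[1 - Phi(2.2414/sqrt(1 + 21 tau^2/(1 - ICC)))]. For example, with ICC 0.02 and tau^2 = 0.02, the ratio is 1 + 0.42/0.98 = 1.429, 2.2414/1.195 = 1.875, and the level is 0.061.

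| r | ICC 0.01 | ICC 0.02 | ICC 0.05 |
|---|---|---|---|
| 1 (tau^2 = 0) | 0.025 | 0.025 | 0.025 |
| 0.9 | 0.028 | 0.032 | 0.043 |
| 0.8 | 0.031 | 0.038 | 0.062 |
| 0.5 (tau^2 = ICC) | 0.042 | 0.061 | 0.122 |

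Simulation (4,000 trials per cell, change-score mixed model with clinic intercept, REML, patient-level df) gave 0.027/0.023/0.025 at r = 1, 0.034/0.040/0.063 at r = 0.8 and 0.036/0.060/0.119 at r = 0.5. A t-test on the 16 clinic-specific moderator effects (14 df) stayed between 0.021 and 0.029 in every cell. With a 20/80 moderator and r = 0.5, the formula gives 0.035/0.047/0.086.

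**Step 6: heterogeneity that doubles the level.** The variance ratio must be (2.2414/1.960)^2 = 1.308. Taking the sampling variance of a clinic's moderator effect as 4/84 (patient variance 1), tau^2 = 0.308 x 4/84 = 0.0147, an SD of about 0.12. For comparison, clinic mean change has an SD of 0.10/0.14/0.22 at the three ICCs.

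**The case against.** The strongest objection is that the size rests on a quantity the documents never give. The ICCs in section 9.2 describe clustering of the outcome, not variation in the moderator's effect. With no variation there is no inflation, and at r = 0.9 the level stays below twice nominal across the whole ICC range. Table 9 may simply be the main-effect formula with 21 put in for the sample size, not a considered assumption about tau^2. All of this stands, and it limits the claim about size. It does not remove the mismatch: the power table and the analysis model imply different standard errors whichever was intended.

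The inherited AIC search is not a closed list and could admit another structure. But it names no moderator term, and data-driven selection does not protect a pre-specified test. Section 9.2 also calls the purpose prudent exploration, which softens the matter, although sections 1.2 and 3 speak more firmly.

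Three stronger readings are tempting, and the documents do not support them:

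- A reader might infer that false moderation claims run at a fixed multiple of 0.025, such as two to four times. That needs tau^2. Even at tau^2 = ICC the multiples are 1.7, 2.4 and 4.9.
- A reader might infer that the test's null is that the moderator effect is the same in every clinic. The null is beta_6 = 0. Homogeneity within an arm is an assumption behind the p-value.
- A reader might extend the figures to the adherence moderation model ("we will fit a generalized linear model with a random effect for clinic and cumulative logit link function"). Nothing was calculated for it.

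**Conclusion.** The concern holds in conditional form. As specified, the beta_6 test omits the clinic-level variance that a cross-level interaction needs, and its 0.025 level is secure only if the moderator's effect on change does not vary between clinics within an arm. Table 9 and the section 9.6 model describe different tests: the table fits tau^2 = ICC on about 9 df, and the model sets that variance to zero.

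The actual level runs from 0.025 (no heterogeneity) to about 0.042/0.061/0.122 at ICC 0.01/0.02/0.05 if tau^2 equals the ICC. These figures assume an even moderator split, 84 completers per clinic and over-time correlation 0.5. An uneven split reduces the inflation. The point concerns the Aim 2 linear model for pain interference and function only. It is worth correcting before analysis because these tests have their own decision rule and the correction is small.

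**What to change.** In the Aim 2 linear model, pre-specify a clinic-level random moderator-by-follow-up effect. State that it is kept regardless of AIC, and test beta_6 on clinic-level degrees of freedom. Name a fallback for non-convergence with 16 clinics: estimate each clinic's moderator effect on change and compare 8 with 8 by a t-test on 14 df. State in section 9.2 that Table 9 assumes a between-clinic moderator variance equal to the ICC, or recompute it under a stated value.

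The cost is a few lines of SAP text and one random term. If moderator effects do not vary between clinics, some power is lost: in simulation, for a 0.30 SD interaction, from about 65% to about 57% with the unweighted fallback (moderator prevalence varying from 30% to 70% between clinics). If tau^2 equals the ICC, the detectable effects after the change are 0.486/0.525/0.628 on 9 df, essentially those already in Table 9.

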8. CLINIC DISCONTINUATION

While our goal is to not have any clinics discontinue, clinic discontinuation could occur by a clinic informing us that they were dropping out after randomization but before training and rollout of pathways or after rollout of pathways or some other unplanned circumstance. It is important to note that our design allows for additional sites to be added in the 2nd round of cluster randomization if site(s) from the first round discontinue or have lower than expected recruitment rates. This is described in more detail in Section 9 (Statistical Considerations).

One of the eligibility criteria for clinics is that the volume of back patients seen on a weekly basis is on average 8 -12 so that over a 6-month period assuming a 50% referral rate (4-6 referred per week) clinics can meet recruitment goal of 105 Veterans referred to their pathway; it may take clinics with smaller patient volumes or lower referral rates longer to enroll and weekly referrals could vary from 2 to 4 per week and we can still meet recruitment goals on our timeline.

Given that this is a embedded pragmatic trial and “enrollment” is controlled by referrals from primary care providers to the clinics randomized pathway either CCP or ICP, the study team will monitor care pathway volume monthly at each participating clinical site. The goal to monitoring pathway volume will be for the study team to trouble-shoot problems to help clinics increase pathway volume. Over the first couple of quarters of an enrollment period at a clinic we will review number of referrals with clinics to make sure meeting goals and to trouble-shoot any problems or issues. If it appears that lower than expected volume is occurring mitigating steps will include meeting with site leaders to review care pathway procedures, trouble-shoot, and enhance education outreach for referring providers. At the time that we begin enrolling block 2 clinics, we will add additional clinics if any has dropped out in block 1 and we will examine recruitment in the clinics in block 1 and determine whether we need to enroll and randomize additional clinics in block 2 to compensate for low recruitment (below target of 105 per clinic) at any of the block 1 clinics. The blocked covariate constrained randomization balances covariates within and across blocks. We will use any information from the enrollment process of the 10 clinics in block 1 to inform and improve the enrollment process for the set of clinics for block 2.

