The standardized effect sizes⁵¹ that we are powered to detect range from 0.30 to 0.50 for the primary outcomes on the administrative sample. This range maps to differences of approximately 2.4 to 5.0 points in the PROMIS Pain Interference score between arms assuming standard deviations in the range found in the pilot study from [name] et al.³³ These magnitude of differences have been reported to be clinically relevant.⁵² Similarly for the survey sample, the range of effect size differences we can detect map to differences of approximately 3.0 to 5.5 points between arms.

For AIM 2, the subgroup analyses of the primary outcomes in the administrative sample, if we assume an even distribution of a binary moderator (e.g. opioid use), our effective sample size for detection of moderation is a quarter that for the main effect analysis yielding an effective sample size of n=336 (21 per clinic).⁵³ For the moderator interaction effect, we can detect medium to large effect size differences over a range of assumptions (**Table 9 below**), which allows for prudent exploration of treatment moderation.

Table 9. Minimum detectable effect size differences by a binary moderator for 90% power, alpha of 0.025 and ICC of 0.01, 0.02, and 0.05 for administrative sample.

Number of clinics per condition	Number of patients per clinic needed at post-intervention follow-up (Total N)	Minimum Detectable Effect Size Difference ICC=0.01	Minimum Detectable Effect Size Difference ICC=0.02	Minimum Detectable Effect Size Difference ICC=0.05	Number of patients per clinic needed at baseline with 20% attrition (Total N _b)
8	21 (N=336)	0.48	0.53	0.63	27 (N _b =432)

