9.6 Data Analyses

Aim 1 Analyses

The primary outcomes are continuous and will be ascertained at the planned baseline and follow-up assessment (3 months) from administrative data collected from the EHR on all eligible LBP Veterans presenting at participating clinics. Changes in pain interference and/or physical function scores will be estimated and the primary hypotheses tested via hierarchical linear mixed-effects models with patients nested within clinics and baseline and 3 month values in the response vector.⁵⁵ Hierarchical linear models are a flexible and powerful analytic tool for clustered longitudinal continuous outcomes. The fixed-effect portion of the model will have the form: $Y_{ijk} = \beta_0 + \beta_1 * (followup) + \beta_2 * (followup * intervention)$ for clinic i , patient j , at time k . Random effects (clinics and time by clinics) will be included in the model to account for clustering of patients within clinics as the clinics are the unit of randomization, random effects will also be included to account for the within-patient correlation between repeated measures over time. We will assess the best fitting random effects structure by fitting a variety of random coefficient models (e.g., random intercept only, random intercept and linear slope) and assess using Akaike Information Criteria (AIC) model selection criteria.^{56,57} The predictors in the model will include a time effect and indicator variables for treatment interacting with the time effect. The intraclass correlation capturing the relationship of outcomes between patients seen at the same clinic is accounted for via the random effects for the clinics and time by clinics, which are assumed to be normally distributed. The model will be fit in the SAS procedure PROC MIXED using full likelihood approximation and the hypotheses will be tested by whether the estimated coefficient β_2 is positive and significantly different than 0 at the 0.025 level due to 2 primary outcome variables. We will include covariates used in the covariate constrained randomization⁴ (5 potential variables; average pain scores, clinic location (main medical center/community clinic), number of participating primary care providers, average level of opioid exposure of LBP patients at clinic, and average age of LBP patients at clinic) in our primary model as well as a limited number of patient-level covariates that are readily available in the EHR (age, gender, race and a comorbidity measure). While we have procedures in place to monitor timing of the 3-month follow-up assessment in the EHR, if we have a significant number of assessments outside the 1-month window for the 3-month assessment that are dropped from the primary analysis, we will conduct a sensitivity analysis including the assessments outside the window and estimating a 3-month treatment effect from this model.

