The survey outcomes for the enrolled subset of patients will be collected at baseline, 3, 6, 9, and 12 months and will include pain interference, function, intensity, catastrophizing, sleep, and depression (see Section 10 for full descriptions). These are all longitudinal continuous outcomes and a hierarchical linear model similar to that described for the primary aim will be fit. We will fit random coefficient models as described above (e.g. random intercept only, random intercept and linear slope) and assess using AIC model selection criteria to determine best model for the covariance structure. Similarly, we will determine the best model for the mean structure (e.g. linear, quadratic, dummy coding) as there are five outcome measurement occasions guided by descriptive plots and model fit assessed using AIC model selection criteria. Due to the timing of administration of baseline surveys that some baseline surveys may occur after the initial intervention contact, we will conduct sensitivity analysis treating baseline surveys after initial provider contact as occurring in the post-treatment period.

Aim 2 Analyses

As highlighted in the UG3 section we have strong clinical and scientific rationale to investigate chronic vs. acute LBP and previous opioid use vs. opioid naïve as *a priori* subgroups for treatment moderation.³⁸ We will define “chronic low back” as pain that has persisted for at least 3 months and resulted in pain on at least half the days in the past six months to be consistent with the NIH task force definition.⁴⁹ All participants will have chronicity of back pain assessed via the EHR template (see Section 6) at the time of initial referral to a given care pathway using questions specified in the NIH minimum dataset.⁴⁹ Opioid exposure prior to pathway entry will be defined as being prescribed at least one prescription opioid for 20 or more consecutive days (yes or no within 12 months prior to entering pathway).⁶⁴ This definition could be altered if different ones are suggested for use by the PMC3. These data will be obtained through VA’s Pharmacy Benefits Management System.

For the planned subgroup analyses for key moderators on the primary outcomes of pain interference and function will be the same modeling framework as described for AIM 1 with the addition of the indicator variable(s) for the moderator and associated interactions.⁶⁵ The fixed-effect portion of the model will have the form: $Y_{ijk} = \beta_0 +$

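### The Aim 2 moderator model omits the intervention main effect, so the tested three-way term depends on the 0/1 coding and takes in part of any baseline difference between arms

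*Combined protocol and SAP*

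**What the plan says.** Section 9.6 specifies the primary (Aim 1) model with follow-up and follow-up-by-intervention as its only design terms: "The predictors in the model will include a time effect and indicator variables for treatment interacting with the time effect". There is no intervention main effect, so both arms share one baseline mean for all patients.

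For Aim 2, the same section says that the moderator analysis "will be the same modeling framework as described for AIM 1 with the addition of the indicator variable(s) for the moderator and associated interactions". The displayed fixed effects run without a gap from beta_0 to beta_6: intercept, moderator, moderator-by-intervention, follow-up, follow-up-by-intervention, moderator-by-follow-up, and the three-way term. Moderation is declared from beta_6 at 0.025: "Differential change in pain interference or function by moderator for the two intervention groups is supported if the coefficient for" the three-way term is significantly different from zero. The moderators are LBP chronicity and prior opioid exposure. The plan does not say which level of either is coded 1.

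Section 9.2 sizes this test in Table 9 (detectable differences of 0.48/0.53/0.63 SD) and comments that the size is one "which allows for prudent exploration of treatment moderation".

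**The concern.** With a 0/1 indicator, the model as written sets the baseline arm difference to zero where the moderator is 0 and estimates it freely where the moderator is 1. Aim 1 constrains it for everyone; a full factorial would constrain it for no one. No reason is given for constraining one subgroup only.

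Two things follow. First, because (1 - moderator) x intervention = intervention - moderator x intervention, and intervention is not in the model, swapping the reference level fits a different model. The size and p-value of beta_6 then change, not only its sign. Second, a baseline arm difference common to both subgroups does not cancel out of beta_6.

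Such a difference is possible here. Clinics are randomized first. Patients enter afterwards through a process that "is controlled by referrals from primary care providers to the clinics randomized pathway either CCP or ICP" (Section 8), and they count once "referred to one of the two arms of the trial with initial contact with pain navigator or central delivery for data collection" has taken place (Section 9.3). Recruitment and delivery staff are unblinded (Section 9.2.1). If ICP patients were worse at baseline in both subgroups, ICP would look relatively better in the subgroup coded 1. If chronic and opioid-exposed are coded 1, that is the direction hypothesized in Section 3. If ICP patients were better at baseline, the bias would run the other way.

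**Working it through.** **Inputs.** From Section 9.2: 8 clinics per arm (g = 8), 84 patients per clinic at follow-up, an even moderator split (n = 42 per subgroup per clinic), ICC 0.01/0.02/0.05, over-time correlation r = 0.50 ("We assumed over time correlations of 0.50 for both patients"), and alpha 0.025. Two-sided testing is from Section 9.3. The patient-level random effect is carried over from the Aim 1 model. Total variance is 1 and no covariates are fitted. Results below are in the order ICC 0.01/0.02/0.05.

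**Reproducing Table 9.** With m = 21 and 9 df (2 x 7 clinics less 5 covariates), the detectable difference is (t[0.9875] + t[0.90]) x sqrt(4[(1-ICC)(1-r) + m ICC (1-r)]/(mg)). At ICC 0.01 this is (2.685 + 1.383) x sqrt(4 x 0.60/168) = 4.068 x 0.1195 = 0.486. All three are 0.486/0.525/0.628, against the stated 0.48/0.53/0.63. The inputs are therefore read correctly, and Table 9 is not affected by this point.

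**What beta_6 estimates.** Let B0 and B1 be the baseline arm differences (ICP minus CCP) in the subgroups coded 0 and 1, and F0 and F1 the differences at 3 months. The model sets E(B0) = 0 and leaves B1 free. Generalized least squares then gives

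beta_6 = F1 - F0 - B1 + c B0, with c = (r s + ICC)/(s + ICC) and s = (1-ICC)/n.

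| Model | Weight on B0 | Weight on B1 |
|---|---|---|
| As written | 0.65/0.73/0.84 | 1 |
| Delete moderator-by-intervention | 0.50 | 0.50 |
| Add intervention main effect | 1 | 1 |

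Only the model as written treats the two subgroups differently.

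**Common baseline difference D.** If F0 and F1 are equal they cancel, so the bias is -(1-c)D whether D persists, halves or vanishes by 3 months. The absorbed share is 1 - c = (1-r)s/(s + ICC):

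- ICC 0.01: s = 0.99/42 = 0.02357; 0.5 x 0.02357/0.03357 = 0.351
- ICC 0.02: s = 0.98/42 = 0.02333; 0.5 x 0.02333/0.04333 = 0.269
- ICC 0.05: s = 0.95/42 = 0.02262; 0.5 x 0.02262/0.07262 = 0.156

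**Sensitivity of the share.**

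| Setting | ICC 0.01/0.02/0.05 |
|---|---|
| r = 0.3 | 49/38/22% |
| r = 0.7 | 21/16/9% |
| Assumed 25/59 split, smaller subgroup coded 0 | 40/33/22% |
| Assumed 25/59 split, larger subgroup coded 0 | 31/23/12% |
| 105 at baseline, 20% attrition | 33/24/13% |
| Only the clinic-level random effects named in the Aim 2 text | 70/54/31% |

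**Standard errors of beta_6.**

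- Main effect added: sqrt(8(1-r)(1-ICC)/(ng)) = 0.1086/0.1080/0.1063
- Term deleted: sqrt(4(1-r^2)(1-ICC)/(ng)) = 0.0940/0.0935/0.0921
- As written: variance is the main-effect-added variance less (1-c)^2 x (2/g)(s + ICC). At ICC 0.01 this is 0.01179 - 0.1232 x 0.00839 = 0.01075, so the SEs are 0.1037/0.1043/0.1043

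**Illustration, D = 0.2 SD (assumed).** Spurious beta_6 is -0.070/-0.054/-0.031. At ICC 0.01 the shift is 0.0702/0.1037 = 0.677 SE, and with critical value 2.241 the rejection rate is Phi(-1.564) + Phi(-2.918) = 6.1%. False-positive rates against 2.5%:

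| D | Normal reference | t, 9 df |
|---|---|---|
| 0.2 SD | 6.1/4.5/3.2% | 5.2/4.0/3.0% |
| 0.1 SD | 3.3/3.0/2.7% | 3.1/2.9/2.6% |

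Under either repair the bias is 0 and the rate 2.5%.

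**Coding dependence.** With no baseline shift, the as-written estimates under the two codings correlate 0.875/0.895/0.932. They disagree on significance in 2.5/2.3/1.9% of null trials. In one simulated data set (ICC 0.02, true beta_6 of 0.2) the p-value was 0.032 under one coding and 0.011 under the other. The full factorial gave 0.028 under both.

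**The case against.** The strongest reply is that the harm is conditional and small. No document says that the arms will differ at baseline, by how much, or in which direction. Several features make it less likely: common training in referral criteria (Section 4.1), patients and providers who know nothing of the other pathway (Section 6.3), constrained randomization on clinic-average pain, opioid exposure and age (Section 9.2.1), and covariate adjustment (Section 9.6). At 0.1 SD the false-positive rate hardly moves. Section 9.2 maps 0.30 to 0.50 SD to 2.4 to 5.0 points, which implies an SD of about 8 to 10 points. The 0.2 SD illustration is then a bias of only about 0.25 to 0.7 points. The coding matters for error control only if it is chosen after seeing the data. Aim 2 is a secondary objective.

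Neither repair is better in every case. For a 0.2 SD difference confined to one subgroup:

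| Model | Difference persists | Difference halves |
|---|---|---|
| Term deleted | +/-0.100 SD; about 12% false positives (normal) | 0; 2.5% |
| Main effect added | 0; 2.5% | +/-0.100 SD; about 9.5% (normal) |
| As written, in coded-0 subgroup | -0.070/-0.054/-0.031 SD | +0.030/+0.046/+0.069 SD |
| As written, in coded-1 subgroup | 0 | -0.100 SD; about 10% (normal) |

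These points limit the size and urgency of the concern. They do not justify the model. Constrained randomization balances clinic averages beforehand, not who is referred afterwards. The displayed model still differs from the framework that it is said to extend. If the omission is a slip, a programmer cannot tell which repair was meant, and the two differ by a third in the variance of beta_6 (0.01179/0.00884 = 1.33).

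**Conclusion.** The concern holds. The Aim 2 model is misspecified against its own stated framework, and its decision coefficient depends on a coding that the plan leaves unstated. Of the three candidate models, only the one as written turns a common baseline arm difference into apparent moderation. The share is 16 to 35% at the plan's ICCs, an even split, correlation 0.50 and a patient random effect, and 13 to 33% with the planned attrition.

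The bias requires a systematic baseline arm difference whose size the documents do not give; the 0.1 and 0.2 SD figures are assumptions. Without one, and with the coding fixed in advance, beta_6 is unbiased and the error rate is 2.5%. The effect is modest, and Aim 1 and Table 9 are untouched. It should be corrected before analysis because this is an a priori test at 0.025 and the correction costs almost nothing.

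**What to change.** Choose one of two models as primary for Aim 2, report the other as a sensitivity analysis, and state which level of each moderator is coded 1.

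1. **Delete moderator-by-intervention.** This is the direct extension of Aim 1. It lowers the SE of beta_6 by 9 to 12% against the model as written (7 to 13% at a 25/59 split). It is exposed to a baseline difference in one subgroup that persists.
2. **Add the intervention main effect.** This is the full factorial. It raises the SE by 2 to 5% (1 to 8% at 25/59). It is exposed to a baseline difference in one subgroup that regresses toward zero.

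Either makes the test independent of the coding and unaffected by a common baseline difference. The documents do not settle which one-subgroup pattern is likelier, so the sponsor should justify the choice. At ICC 0.01 and an even split, both SEs (0.094 and 0.109) stay below the 0.118 implied by Table 9 (0.48/4.068), so the stated power is not at risk there.

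The cost is one model term and one sentence on coding, with no change to data collection or sample size.
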